9.9 Post-Treatment Follow-Up

All study subjects will have follow-up assessments at 1, 3, 6, 12, 18, and 26 weeks after injection day to evaluate effectiveness of the treatment and to assess AEs and protocol compliance. The Blinded Evaluator will evaluate the clinical status of the Subject at each visit.

At least 48 hours prior to the visit, the Subject will be reminded of the visit date and time, the need to abstain from acetaminophen for at least 48 hours prior to each follow-up visit and the requirement to bring their Subject Electronic Diary and the acetaminophen for a pill count with them to the appointment.

If the Subject arrives for a study visit without discontinuing acetaminophen for at least 48 hours prior to the visit, the visit should be rescheduled within the allowed study window. Study assessments should be performed as soon as possible and the protocol deviation, if applicable, recorded in the source and eCRF. The Subject must be re-educated about the importance of protocol compliance.

If the Subject does not come in at the expected time, at least three attempts will be made to contact the Subject in order to accomplish maximum Subject compliance with the follow-up schedule.

The following post-treatment visits will be performed. The Subject will be asked whether any concomitant medications have been taken. All assessments will be done by the Blinded Evaluator.

9.9.1 1 Week ± 3 Days

- Concomitant Medications
- Assess Adverse Events
- Confirm Rescue Medication Washout
- Count/Dispense Rescue Medication Pills (if needed)
- Evaluate Subject Electronic Diary
- Physical Evaluation (Both Knees) to be performed by Blinded Evaluator
- ROM (Index Knee) to be performed by Blinded Evaluator
- Evaluator Global Assessment to be performed by Blinded Evaluator
- WOMAC (Both Knees)
- VAS Pain Scale (Both Knees)
- NRS Pain Scale (Both Knees)
- EuroQoL-5D-5L
- Patient Global Assessment

9.9.2 3 Weeks ± 3 Days

- Concomitant Medications
- Assess Adverse Events

- Confirm Rescue Medication Washout
- Count/Dispense Rescue Medication Pills (if needed)
- Evaluate Subject Electronic Diary
- Physical Evaluation (Both Knees) to be performed by Blinded Evaluator
- Evaluator Global Assessment to be performed by Blinded Evaluator
- ROM (Index Knee) to be performed by Blinded Evaluator
- WOMAC (Both Knees)
- VAS Pain Scale (Both Knees)
- NRS Pain Scale (Both Knees)
- EuroQoL-5D-5L
- Patient Global Assessment

9.9.3 6 Weeks ± 3 Days

- Concomitant Medications
- Assess Adverse Events
- Confirm Rescue Medication Washout
- Count/Dispense Rescue Medication Pills (if needed)
- Evaluate Subject Electronic Diary
- Physical Evaluation (Both Knees) to be performed by Blinded Evaluator
- Evaluator Global Assessment to be performed by Blinded Evaluator
- ROM (Index Knee) to be performed by Blinded Evaluator
- WOMAC (Both Knees)
- VAS Pain Scale (Both Knees)
- NRS Pain Scale (Both Knees)
- EuroQoL-5D-5L
- Patient Global Assessment

9.9.4 12 Weeks ± 3 Days

- Concomitant Medications
- Assess Adverse Events
- Confirm Rescue Medication Washout
- Count/Dispense Rescue Medication Pills (if needed)
- Evaluate Subject Electronic Diary
- Physical Evaluation (Both Knees) to be performed by Blinded Evaluator
- ROM (Both Knees) to be performed by Blinded Evaluator
- Evaluator Global Assessment to be performed by Blinded Evaluator
- WOMAC (Both Knees)
- VAS Pain Scale (Both Knees)
- NRS Pain Scale (Both Knees)

- EuroQoL-5D-5L
- Patient Global Assessment

9.9.5 18 Weeks ± 7 Days

- Concomitant Medications
- Assess Adverse Events
- Confirm Rescue Medication Washout
- Count/Dispense Rescue Medication Pills (if needed)
- Evaluate Subject Electronic Diary
- Physical Evaluation (Both Knees)
- ROM (Index Knee) to be performed by Blinded Evaluator
- Evaluator Global Assessment to be performed by Blinded Evaluator
- WOMAC (Both Knees)
- VAS Pain Scale (Both Knees)
- NRS Pain Scale (Both Knees)
- EuroQoL-5D-5L
- Patient Global Assessment

9.9.6 26 Weeks ± 7 Days

- Concomitant Medications
- Assess Adverse Events
- Confirm Rescue Medication Washout
- Count Rescue Medication Pills
- Evaluate Subject Electronic Diary
- Physical Evaluation (Both Knees)
- ROM (Both Knees) to be performed by Blinded Evaluator
- Evaluator Global Assessment to be performed by Blinded Evaluator
- WOMAC (Both Knees)
- VAS Pain Scale (Both Knees)
- NRS Pain Scale (Both Knees)
- EuroQoL-5D-5L
- Patient Global Assessment

9.9.7 Early Termination due to lack of efficacy in the Index knee

If a subject wants to obtain additional treatments such as HA and steroid injection in Index knee, the subject should undergo below assessment before receiving the additional treatment:

- Concomitant Medications
- Assess Adverse Events

- Confirm Rescue Medication Washout
- Count Rescue Medication Pills
- Evaluate Subject Electronic Diary
- Physical Evaluation (Both Knees)
- ROM (Both Knees) to be performed by Blinded Evaluator
- Evaluator Global Assessment to be performed by Blinded Evaluator
- WOMAC (Both Knees)
- VAS Pain Scale (Both Knees)
- NRS Pain Scale (Both Knees)
- EuroQoL-5D-5L
- Patient Global Assessment

After completing the assessment, the subject should be terminated from the study. These subjects will be considered as Treatment Failure.

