2 DEFINITIONS

Baseline: The assessments performed prior to the study injection after the Screening Visit.

Blinded Evaluator: The Blinded Evaluator will be a physician, research nurse, registered physiotherapist or physician assistant trained by the Principal Investigator (PI) to perform the assessments outlined in the protocol. The Blinded Evaluator will complete the Physical Exam, Physical Evaluation of both knees, Range of Motion (ROM) assessment of both knees, and the Evaluator Global Assessment.

End of Study: End of study is defined as the last subject's last visit.

Enrolled: A Subject who has signed the informed consent form (ICF) is enrolled.

Index Knee: The knee that meets the eligibility criteria for treatment. The Index knee may also be termed the "study knee". In subjects with bilateral knee Osteoarthritis (OA), where both knees meet eligibility criteria, the more symptomatic knee is the Index knee.

Institutional Review Board (IRB) refers to an independent body (e.g. Research Ethics Boards, Independent Ethics Committees) whose responsibility is to ensure the protection of rights, safety and well-being of human subjects involved in a trial. Committees with these responsibilities will be referred to in this document as IRB.

Rescue Medication: Acetaminophen will be distributed as the rescue medication. It is the only medication that should be taken for knee pain during the entire study. Rescue medication will be discontinued at least 48 hours prior to Baseline and all follow-up visits.

Treating Physician: The Treating Physician will most often be the PI. He/she will administer the Cingal[®], Triamcinolone Hexacetonide (TH), or Placebo injection but will not participate in the efficacy evaluation.

Treatment Failure: A Subject who undergoes a procedure or uses a medication (other than the rescue medication) for the treatment of OA in the Index knee at any time after the study injection through the 26-week visit.

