15.9 Protocol Adherence

The Investigator agrees to conduct the study according to the protocol and agrees that all persons delegated to perform study procedures will do so as well. The Investigator must read the protocol thoroughly and must follow the instructions exactly. Investigators shall propose to Anika Therapeutics, Inc. any appropriate modifications to the Protocol or of the use of the CTM. Any change should be agreed to by prior discussion between Anika Therapeutics, Inc. and the Investigator, with written protocol amendments made prior to affecting the changes agreed upon. The Investigator is not to conduct any protocol modifications without prior written permission from Anika Therapeutics, Inc. Investigator will refrain from implementing any modifications to the protocol without agreement from the Sponsor, IRB and FDA, if applicable. Each Investigator will be responsible for enrolling only those subjects who have met protocol eligibility criteria.

Deviations from the protocol include, but are not limited to, the use of prohibited medications or therapies, out of window visits, etc. All protocol deviations should be documented and explained. Major protocol violations are defined as those that could impact the efficacy evaluation such as a Subject is ineligible, missing key data, received an unauthorized treatment, etc. All subjects with protocol deviations will continue to be followed for safety and efficacy assessments. Analysis of study data will be done on both the ITT and PP populations.

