15.20 Subject Withdrawal

Each Subject is free to discontinue from the study at any time, for any reason. If a Subject discontinues the study, the Investigator will record the reason for withdrawal on the eCRF. Examples of reasons for premature withdrawal of a Subject from the study include:

- Inter-current illness that would, in the judgment of the Investigator, affect study assessment to a significant degree
- Subject noncompliance with follow-up assessments
- Subject request to withdraw
- Subject lost to follow-up
- Treatment failure
- Termination of the site's study participation by Anika Therapeutics, Inc., the institution, IRB or the Regulatory Authority
- Other (reason to be documented in the eCRF)

Every effort shall be made to have withdrawn subjects return for the required safety evaluations as detailed in the protocol.

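### Protocol 9.9.7 ends efficacy follow-up when a subject wants added index-knee treatment, so week-26 WOMAC pain goes missing for lack of efficacy and is imputed under a MAR rationale that assumes otherwise

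*Protocol*

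**What the plan says.** Protocol 9.9.7, whose title names lack of efficacy in the index knee, sets its condition as "If a subject wants to obtain additional treatments such as HA and steroid injection in Index knee". The subject has a full assessment first, including WOMAC, VAS, NRS and both global assessments. Then: "After completing the assessment, the subject should be terminated from the study". The section adds "These subjects will be considered as Treatment Failure".

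Protocol 15.20 lists "Treatment failure" among the reasons for withdrawal and asks that withdrawn subjects be brought back for safety evaluations. It does not mention efficacy.

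Protocol 15.9 deals with a neighbouring case. "Major protocol violations are defined as those that could impact the efficacy evaluation", and its examples include "missing key data, received an unauthorized treatment". It continues: "All subjects with protocol deviations will continue to be followed for safety and efficacy assessments". A subject who has already taken such treatment also counts as a Treatment Failure under section 2, which defines one as "A Subject who undergoes a procedure or uses a medication (other than the rescue medication) for the treatment of OA in the Index knee". That definition covers the whole period from injection to the 26-week visit.

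The primary endpoint is change in WOMAC pain at week 26. SAP 4.1.2 fits the model to the week-26 records only. Protocol 11.8 and SAP 4.5 specify ITT with multiple imputation from a mixed effects repeated measures model. SAP 4.5 justifies MAR by reasoning that these subjects' missing data will probably not stem from the treatment working or failing, and it cites a missing rate below 1% in previous studies.

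**The concern.** The plan creates by rule the kind of missing value that its missing-data rationale says is unlikely. A 9.9.7 exit happens because the injection did not give enough relief, and the missing week-26 score follows directly from it.

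In a trial of repeated dosing, leaving the study and stopping the drug often go together. Here the only dose was given on day 0, so terminating the subject gains nothing on exposure and gives up the remaining outcome data.

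What is at stake is the Cingal versus TH estimate and its 95% CI. The protocol calls the trial a pilot without formal hypothesis testing, although the SAP also lists hypotheses and p-values. Imbalance between arms is plausible on the trial's own rationale: the Introduction describes steroid relief as short term and relief from the cross-linked HA product as lasting up to 26 weeks. If that is right, 9.9.7 exits need not be equally common in the arms.

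**Working it through.** **1. The plan's own figures.** Inputs from Protocol 11.1: 99 per arm for Cingal and TH, SD 20, differences of 8 and 10 points; two-sided 5% level.

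- Standard error of the difference = 20 × √(2/99) = 2.84 mm.
- Power at 8 = Φ(8/2.84 − 1.96) = 80.4% (80.0% with the noncentral t). The stated 80% reproduces.
- Power at 10 = 94.0%. The stated figure of over 90% reproduces. Both assume no dropout.
- Planned 95% CI half-width = 1.96 × 2.84 = 5.57 mm. This is the yardstick below.

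**2. What happens to a subject who exits at, say, week 12.** The exit WOMAC is recorded under the early-termination visit. There are no week-18 or week-26 visits. The week-26 record that SAP 4.1.2 needs is absent, so it is imputed. Neither document says whether the exit WOMAC enters the imputation model or carries it to week 26, and none of the planned analyses departs from MAR. An exit within 7 days of week 26 need not lose the value.

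**3. Which scores can still be obtained.**

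- *Week-26 pain without added treatment:* can be imputed, and MAR given observed pain is arguable if the exit WOMAC is in the model.
- *Week-26 pain regardless of added treatment:* never observed after exit. It can only be approximated by assumption, for example with reference-based or delta-adjusted imputation.

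**4. Size.** Let f be the share of an arm that exits under 9.9.7, and G the mean gap, among those who exit, between the imputed score and the score that would have been observed on other treatment. The two versions of the contrast then differ by

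shift = G × (f in one arm − f in the other).

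The documents give neither f nor G. G is assumed to be 10 to 30 mm.

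| Scenario | Shift | Share of 5.57 mm |
|---|---|---|
| Equal exit shares | 0 | 0% |
| Shares differ by 5 points (assumed) | 10 × 0.05 = 0.5 to 30 × 0.05 = 1.5 mm | 9% to 27% |
| Under 1% in each arm; at most 1% vs 0% | 10 × 0.01 = 0.1 to 30 × 0.01 = 0.3 mm | 2% to 5% |
| About 1% overall (0.01 × 231 = 2.3), with 2 subjects both in one arm of 99 (2/99 = 2.0%) | 0.2 to 0.6 mm | 4% to 11% |

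These are scenarios, not bounds.

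**The case against.** The strongest defence is that stopping before added treatment is a coherent choice. The objective is to separate what TH contributes within Cingal from TH alone. A TH subject who then receives HA has had both component classes of Cingal, so a later score blurs that contrast. On this view a target without added treatment is the right one, the assessment required by 9.9.7 supplies the information for it, and the shifts above are only distances between two targets. This largely stands as a defence of that target. But the plan does not state the target or say that the exit score is used. Collecting later scores would not harm it either: Protocol 9.2.6 records medication start dates, so those scores can be set aside.

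A second defence is the SAP's missing rate below 1%. At that rate with equal arms the effect is negligible. The documents do not show whether the previous studies had a similar exit rule, so the rate may not carry over.

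Three stronger readings are tempting, and the documents do not support them.

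- *MAR must fail.* It need not, if the model conditions on the exit WOMAC. What fails is the reason SAP 4.5 gives for MAR.
- *A contrast regardless of added treatment is out of reach in every form.* Only its direct observation is lost; approximation by stated assumptions remains possible.
- *Protocol 15.9 and 9.9.7 together distort the contrast by mixing observed and imputed scores differently by arm.* They address different events: treatment already received, and treatment wanted but not yet given. If sites follow 9.9.7 and 15.20 as the specific rules, all failures leave and nothing is mixed. Subjects and evaluators are blinded, and nothing in the documents suggests routing that differs by arm, so no size can be attached to this.

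**Conclusion.** The point holds as a design weakness that is cheap to remove. By rule, 9.9.7 turns lack of efficacy into a missing primary outcome, with no offsetting reduction in exposure, and the SAP's argument for MAR overlooks this route.

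The size is unknown. It is negligible at the SAP's missing rate with equal arms. It reaches 0.5 to 1.5 mm, or 9% to 27% of the planned CI half-width, only under an assumed 5-point difference in failure shares and an assumed gap of 10 to 30 mm. A reader might infer that the primary estimate is biased by that amount. The documents do not support this, because the shift is bias only if the intended target is pain regardless of added treatment, and the plan names no target. The exit assessment and the week-26 window both reduce the loss. Confidence is medium because no failure rate is given.

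**What to change.** **Protocol.** Keep the pre-treatment assessment in 9.9.7. Replace termination with continuation of the scheduled visits (WOMAC, adverse events, concomitant medication) to week 26 unless the subject withdraws consent. Remove treatment failure from 15.20 as a reason to end follow-up. Access to other treatment is unchanged. Section 15.9 already keeps subjects with deviations in efficacy follow-up, so this extends an existing principle. The prohibition in 9.2.5 can stay, with breaches recorded as deviations.

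**SAP.** State that the exit WOMAC enters the imputation model. Choose one rule for all scores after added index-knee treatment, either used as observed or set to missing and imputed, and run the other as a sensitivity analysis. Tie the rule to the protocol's 26-week Treatment Failure definition plus the 9.9.7 cases. The copy in SAP 4.1.4 stops at week 12 and would miss later failures.

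**Cost.** One protocol amendment, which under 15.4 needs FDA and IRB approval before sites (up to 40) can use it; a short SAP revision; and a few already scheduled visits by subjects on other treatment. No new procedure or additional sample is needed.

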10 ADVERSE EVENTS / ADVERSE REACTIONS

10.1 Definitions - Device Adverse Events

Adverse Event (AE): Any untoward medical occurrence, unintended disease or injury, or untoward clinical signs (including abnormal laboratory findings) in subjects, users or other persons, whether or not related to the investigational medical device

NOTE 1 This definition includes events related to the investigational medical device or the comparator.

NOTE 2 This definition includes events related to the procedures involved.

NOTE 3 For users or other persons, this definition is restricted to events related to investigational medical devices"

Adverse Device Effect (ADE): An AE related to the use of the investigational medical device

NOTE 1: This definition includes Adverse Events resulting from insufficient or inadequate instructions for use, deployment, implantation, installation, or operation, or any malfunction of the CTM.

NOTE 2: This definition includes any event resulting from use error or from intentional misuse of the CTM.

Anticipated Serious Adverse Device Effect: An effect which by its nature, incidence, severity or outcome has been identified in the Investigator's Brochure.

Serious Adverse Event (SAE): Adverse Event that:

- a) led to death,
- b) led to serious deterioration in the health of the subject, that either resulted in
- 1) a life-threatening illness or injury, or
- 2) a permanent impairment of a body structure or a body function, or
- 3) in-patient or prolonged hospitalization, or
- 4) medical or surgical intervention to prevent life-threatening illness or injury or permanent impairment to a body structure or a body function,
- c) led to foetal distress, foetal death or a congenital abnormality or birth defect

NOTE Planned hospitalization for a pre-existing condition, or a procedure required by the CIP, without serious deterioration in health, is not considered a serious adverse event.

Serious Adverse Device Effect (SADE): An adverse device effect that has resulted in any of the consequences characteristic of a serious adverse event.

Unanticipated Serious Adverse Device Event (USADE): Serious adverse device effect which by its nature, incidence, severity or outcome has not been identified in the current version of the risk analysis report.

10.2 Definitions – Drug Adverse Events

Adverse Event (AE): An adverse event (sometimes referred to as an adverse experience) means any untoward medical occurrence associated with the use of a drug in humans, whether or not considered drug related.

Suspected Adverse Reaction (SAR): A suspected adverse reaction means any adverse event for which there is a reasonable possibility that the drug caused the event.

Adverse Reaction (AR): An adverse reaction means any adverse event caused by a drug. Adverse reactions are a subset of all suspected adverse reactions where there is reason to conclude that the drug caused the event.

Unexpected AE/SAR/AR: An adverse event, suspected adverse reaction or adverse reaction is considered "unexpected" if it not listed in the Investigator's Brochure.

Serious AE/SAR/AR: An adverse event, suspected adverse reaction or adverse reaction is considered "serious" if, in the view of either the Investigator or Sponsor, it results in death, a lifethreatening adverse event, inpatient hospitalization or prolongation of existing hospitalization, a persistent or significant incapacity or substantial disruption of the ability to conduct normal life functions, or a congenital anomaly/birth defect. If either the Investigator or Sponsor believes that an event is serious, the event will be considered serious and evaluated by the Sponsor for expedited reporting.

Suspected Unexpected Serious Adverse Reaction (SUSAR): An adverse event, suspected adverse reaction or adverse reaction is considered a SUSAR if it meets the criteria of both "Unexpected" and "Serious" as defined in this section. Any event believed to be a SUSAR by the Investigator and/or the Sponsor will be evaluated by the Sponsor for expedited reporting.

10.3 Relationship

The Relationship between an AE and the CTM and / or the study procedure will be determined by the Investigator on the basis of his or her clinical judgment and the following definitions:

Definitely Related: The AE follows a reasonable temporal sequence from administration of the CTM/study procedure; the AE follows a known or expected response pattern to the CTM/study procedure.

Probably Related: The AE follows a reasonable temporal sequence from administration of the CTM/study procedure; the AE follows a known or expected response pattern to the CTM/study procedure; and the AE could not be reasonably explained by the known characteristics of the

subject's clinical state.

Possibly Related: The AE follows a reasonable temporal sequence from administration of the CTM/study procedure; the AE follows a known or expected response pattern to the CTM/study procedure but could readily have been produced by a number of other factors.

Unlikely Related: The AE which etiology is unlikely related to the CTM/study procedure even if event may follow a known or expected response pattern to the CTM/study procedure, and likely to be produced by a number of other factors. Sufficient information is not available at the time of the AE to determine its causality.

Not Related: An AE for which sufficient information exists to indicate that the etiology is unrelated to the CTM/study procedure. One or more of the following variables apply:

- The AE does not follow a reasonable temporal sequence following administration of the CTM/study procedure;
- The AE is readily explained by the subject's clinical state or other therapies.

For events that are determined to be definitely, probably or possibly related, additional information on the relationship and timing of the event in relation to the arthrocentesis and study injection will be captured.

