11.7 Adverse Events

All AEs will be coded according to MedDRA. Safety assessments will include Treatment-Emergent Adverse Events (TEAEs) which are defined as AEs with an Investigator assessment of definitely,

probably, or possibly related to CTM/study procedure. TEAEs will be summarized with frequencies and percentages by system organ class and preferred term, severity, and relationship to study CTM/study procedure for each treatment arm. In summaries of TEAEs by severity and relationship to CTM/study procedure for subjects reporting multiple episodes, all reported events will be included, not only the worst reported case. Serious Adverse Events will also be presented by relationship to the CTM/study procedure.

The number of subjects with at least one AE will be tabulated for each treatment arm. Differences between the treatment arms will be tested using Fisher's exact test. Then the number of AEs for each treatment arm will also be tabulated.

The number of subjects and the number of AEs will be tabulated by severity, relationship, and local injection site specific events versus non local events.

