13.3.2 Anticipated Adverse Reactions

Reported adverse reactions associated with the IA use of combined Hyaluronic Acid and Triamcinolone Hexacetonide:

Single intra-articular injections of sodium hyaluronate combined with Triamcinolone Hexacetonide has been studied by Anika Therapeutics, Inc. in two Phase III clinical trials: Cingal 13-01, 16-02 and additionally the 39-week extension trial: Cingal 17-02

The most common reported adverse events associated are the following: arthralgia, joint swelling, warmth, range of motion decrease and injection site pain.

Incidences of rash, headache, dizziness, chills, hives, itching, nausea, muscle cramps, peripheral edema, and malaise have also been reported in association with intra-articular injections.

In Cingal 13-01, 16-02, and 17-02 the AEs that were possibly, probably and definitely related to the study injection for patients receiving Cingal were 2.0%, 7.6% and 0 % respectively [14-16]. These AEs were minor or moderate complications that required little or no treatment. These included injection site events, joint swelling, joint pain, and limb pain.

Reported adverse reactions associated with the IA use of corticosteroids:

Single intra-articular injections of Triamcinolone Hexacetonide have been associated with the following adverse reactions:

- Dermatologic: Whitening of the skin at the injection site, local fat atrophy.
- Musculoskeletal: Joint infection, joint swelling and pain several hours after injection, tendon rupture, pain, swelling, ligament damage.
- Neurological: Nerve damage.

• General: Infection, local bleeding, allergic reactions.

Anika Therapeutics, Inc. has conducted one Phase III trial utilizing Triamcinolone Hexacetonide (Lederlon) in Cingal 16-02 and additionally the 39-week extension trial: Cingal 17-02 [14, 15]. The AEs that were possibly, probably and definitely related to the study injection for patients receiving Triamcinolone Hexacetonide were 4.1% and 0 % respectively. These AEs were minor or moderate complications that required little or no treatment. These involved injection site pain and joint pain.

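### Relationship categories in Protocol 10.3 overlap at the line that decides TEAE status, and insufficient information is mentioned only in a category that is not counted

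*Protocol*

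**What the plan says.** Protocol 10.3 has five relationship categories. The rating "will be determined by the Investigator on the basis of his or her clinical judgment and the following definitions". Three definitions meet at the line that matters here:

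- **Possibly Related** requires plausible timing and an expected response pattern, "but could readily have been produced by a number of other factors".
- **Unlikely Related** covers an event judged unlikely to be related "even if event may follow a known or expected response pattern to the CTM/study procedure, and likely to be produced by a number of other" possible causes. It does not mention timing. It ends: "Sufficient information is not available at the time of the AE to determine its causality".
- **Not Related** is "An AE for which sufficient information exists to indicate that the etiology is unrelated to the CTM/study procedure", supported by one or more of two conditions. One is implausible timing. The other reads: "The AE is readily explained by the subject's clinical state or other therapies".

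Protocol 11.7 then uses this line to define TEAEs, "which are defined as AEs with an Investigator assessment of definitely", probably or possibly related. SAP 4.4 has the same rule, referring to the CTM alone. The summaries by system organ class and preferred term are specified for TEAEs. The last paragraph of 10.3 also limits extra detail on relationship and timing, relative to the arthrocentesis and the injection, to events rated definitely, probably or possibly related.

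On the reactions expected, Protocol 13.3.2 says: "The most common reported adverse events associated are the following: arthralgia, joint swelling, warmth, range of motion decrease and injection site pain".

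**The concern.** The step from Possibly to Unlikely or Not Related decides whether an event is counted. Two raters applying the same text to the same event could land on opposite sides, and nothing in 10.3 says which definition prevails.

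The events most exposed are the ones the protocol expects most often. Every subject has symptomatic OA in the index knee, so for arthralgia or swelling soon after the injection the underlying disease is always a candidate explanation.

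Missing information is the second problem. A cause that cannot yet be assessed has not been judged unlikely, yet only Unlikely Related mentions that situation. An event placed there loses its line in the only display planned by event type. It also loses the timing detail that would help someone re-examine it, and later re-tabulation cannot restore data that were not collected.

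The raters are not all blinded either. The Investigator assigns relationship, and Protocol 9.2.22 says the unblinded Treating Physician is most often the PI. Loose definitions leave room for misclassification that differs between arms.

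**Working it through.** No figure in the plan depends on these definitions, so the check is logical, followed by an illustration.

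**1. Definitions coded as written.** Each event was described by five yes/no attributes:
- T: plausible timing
- P: expected pattern
- A: another factor could readily have produced it
- C: readily explained by clinical state or other therapy
- S: sufficient information

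C was taken to imply A. That removes 8 of 2^5 = 32 combinations and leaves 24. The categories were coded as:
- Definitely: T and P
- Probably: T, P and not C
- Possibly: T, P and A
- Unlikely: A and not S
- Not Related: S, and either not T or C

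**2. Result.** Four combinations meet Possibly Related:

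| C | S | Counted categories met | Uncounted category met |
|---|---|---|---|
| no | yes | Definitely, Probably, Possibly | none |
| no | no | Definitely, Probably, Possibly | Unlikely |
| yes | no | Definitely, Possibly | Unlikely |
| yes | yes | Definitely, Possibly | Not Related |

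Three of the four also meet an uncounted category. In the first two rows the only difference is whether information is sufficient. Losing it adds Unlikely and removes no counted category. All three overlapping combinations also meet Definitely Related, because that definition has no alternative-cause clause. Five of the 24 combinations meet no category.

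**3. Limit of the coding.** It lets an alternative factor plus missing information satisfy Unlikely, and sufficient information plus one condition satisfy Not Related. Both definitions also call for a judgment that the cause is unlikely or unrelated. The table shows what the wording permits, not how often raters would use it.

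**4. How small the counts could be.** Protocol 13.3.2 gives related-AE rates in study 16-02 of 7.6% (Cingal) and 4.1% (TH). Assume these are percentages of subjects and apply here, with 99 per arm (Protocol 11.1):
- Cingal: 0.076 × 99 = 7.52
- TH: 0.041 × 99 = 4.06
- Gap: 7.52 − 4.06 = 3.46 subjects

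The documents give no reclassification rate, so two assumed patterns are shown:
- *Same share in both arms, 10% to 50%.* Cingal falls to 6.8 to 3.8 and TH to 3.7 to 2.0. The ratio of the arms does not change.
- *One, two or three Cingal subjects and no TH subjects.* The gap shrinks by 1/3.46 = 29%, 2/3.46 = 58% or 3/3.46 = 87%.

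The second pattern is deliberately one-sided. It shows only that counts of this size are sensitive to a few ratings.

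**The case against.** The strongest reply is that the rating is a clinical judgment and the definitions only guide it. On that view, could readily have another cause and is likely to have another cause are two points on one scale. The information sentence under Unlikely follows a finding that the cause is unlikely, so it may add to that finding and contrast with Not Related rather than open a separate route. Not Related first demands information that the cause is unrelated, so having knee OA does not by itself qualify an event. Protocol 10.5.1 names pain, swelling and inflammation at the injection site as complications of the injection. All of this limits the overlap. It does not supply a tie-break or say where an unassessable event belongs.

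The reply is also right that the consequences are bounded. Protocol 10.5.1 records all AEs whatever their relationship. Protocol 11.7 and SAP 4.4 tabulate subjects with any AE, and subjects and events by relationship. The planned Fisher's exact test follows the any-AE count; no test of related events is specified.

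A reader might infer more than the documents support:
- *That counts are arbitrary and biased low.* Judgment still operates. Only the information sentence has a downward direction, and the loose wording of Definitely Related allows movement the other way.
- *That missing information leads to Not Related.* That category requires sufficient information.
- *That ratings are frozen when the event occurs.* The phrase describes when information is lacking. Protocol 15.15 provides for audited eCRF changes.
- *That the suspension condition in 10.5.4 is weakened.* It needs a probable or definite relationship, which a Possibly rating would not meet either.

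Finally, 10.5.1 uses treatment-emergent by timing while 11.7 uses it by relationship. Reconciling them on timing would remove this line's effect on TEAE entry, but not its effect on the by-relationship table or the extra timing capture.

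**Conclusion.** The point holds in a limited form. The categories are not mutually exclusive at the counted/uncounted line, and insufficient information is mentioned only on the uncounted side. Related-event counts are therefore not reproducible and may understate related events.

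What is affected is the TEAE summaries by system organ class and preferred term, the split by relationship, and the extra timing capture. Recording of AEs and the any-AE comparison are not affected.

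The size and net direction of the overlap effect cannot be derived from the documents. The possible understatement rests on reading the information sentence as a place to put events of unknown cause. That reading is open on the text but not the only one. The illustrative counts rest on the assumptions stated with them and are not an estimate of bias. This is a wording defect in a main safety display, worth correcting because the correction is cheap.

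**What to change.** In Protocol 10.3:

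1. Delete the sentence "Sufficient information is not available at the time of the AE to determine its causality" from Unlikely Related. State instead that an event with insufficient information is rated Possibly Related until information arrives, and that the rating is then updated.
2. Make the two sides exclusive: an event with plausible timing and an expected response pattern is rated Unlikely or Not Related only when specific documented information points to another cause, and underlying knee OA alone is not such information.

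The second sentence leaves room for informed judgment. A well-timed knee event with a documented other cause can still be rated on the uncounted side. A blanket rule that anything meeting Possibly must be rated at least Possibly would remove that, and is not proposed.

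The cost is an edit to 10.3 and matching text in the eCRF completion guidelines. The TEAE definitions in 11.7 and SAP 4.4 need no change for this. The downside is that slightly more events will be counted as related in every arm, so the related-event figures will look slightly less favourable.
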